3.0 Study Endpoints/Events/Outcomes

3.1 Primary Endpoint/Event/Outcome:

Diet quality. Trained research staff certified in collecting dietary recalls using Nutrition Data System for Research software will collect three 24-hour dietary recall interviews (2 weekdays, 1 weekend day) from each participant at each measurement period (baseline and follow up). Dietary recall data will be used to calculate the Health Eating Index-2015 Score. HEI-2015 is a scoring system designed to measure adherence to the 2015-2020 Dietary Guidelines for Americans (2015-2020 DGA).^{69,70}

3.2 Secondary Endpoint(s)/Event(s)/Outcome(s):

Food insecurity. Food insecurity in the past 6 months will be measured with the gold-standard, 18-item food security screening module of the USDA, which will allow for assessment of both binary food insecurity (yes, food insecure; no, food secure) and level of food security (very low, low, marginal, and high food security).⁹¹ We will also use newly developed and validated nutrition insecurity measures to assess **nutrition insecurity** in the past 6 months, which helps us understand fuller contexts around choices people may make when money is tight (e.g., compromise nutrition for a full stomach).¹³⁷

Fruit & Vegetable purchasing outcomes: Participants will record their fruit and vegetable purchases using forms in a provided booklet, and mail their booklets to the researchers in prepaid addressed envelopes, which will be used to measure:

- Average weekly servings of fruits and vegetables purchased
- Total number of trips
- Store types visited

Mobile Market shopping patterns: Participants randomized to the intervention sites will participate in a “Market Members” program, which tracks their purchases at the Mobile Market (i.e. number of transactions, items purchased, dollars spent).

Personal, social, behavioral, and environmental factors that may influence mobile market adoption. These factors include:

- Neighborhood Healthy Food Availability (4 item scale; $\alpha=0.89$);⁹⁹
- Social Connectedness (8 item scale, $\alpha=0.92$);¹⁰²
- Health-related quality of life (4-items);¹⁰³⁻¹⁰⁷
- Self-efficacy of Healthy Cooking (4 item scale, $\alpha=0.85$).¹⁰⁹
- Self-efficacy for eating and cooking fruits and vegetables (4 item scale, $\alpha=0.90$).¹⁰⁸
- Everyday Discrimination Scale (6 item scale $\alpha=0.77$ + 2 follow-up items)¹³⁹⁻¹⁴⁰

Mobile market features that could influence market shopping adoption will be measured at follow-up for participants who were located at intervention site locations. These factors include:

- Perceived convenience of market service
- Whether the market meets participant cultural food needs
- Perceived affordability of market food prices
- Would you recommend the market to a friend (yes/no)?
- Satisfaction of the market's: (a) location and timing; (b) selection of food items available; (c) prices; (d) customer service; and (e) overall shopping experience (not at all satisfied to very satisfied) will also be measured.

Qualitative interview questions. Qualitative interviews will be conducted with a subsample of intervention participants (high and low adopters). Interviews will be audio recorded and occur in person or by phone. Main interview questions will inductively explore factors that influenced market shopping and shopping adoption.

4.0 Study Intervention(s)/Interaction(s)

4.1 Description:

Intervention and waitlist control. Following baseline participant data collection, sites will be randomized to receive the full-service mobile market intervention or serve as the wait list control.

The Full-Service Mobile Market start-up involves two key components.

(1) Initial community engagement: Prior to randomization, community sites will begin engagement activities aligned with CBPR best-practices.¹¹⁵⁻¹¹⁷ These activities include regular meetings with site location staff to develop logistical plans for research activities and market intervention. Following randomization, site group assignment will be revealed for participants and the UMN research team after baseline data collection for the wave is complete, continued site engagement will occur to finalize logistics, including selection of time for the weekly market stop. Resident meetings will be held to introduce how the market works (e.g., when it will come, foods / prices to expect, payment forms accepted). The market schedule will be advertised in community sites (e.g., elevators, community rooms, resident newsletters). Based on our ongoing work, this initial community engagement takes two-weeks to two months, is critical to launching new sites, and is essential for building/maintaining rapport and trust. These activities will be repeated for waitlist sites after follow-up data collection in each Wave.

As a note, this community engagement occurs at new Mobile Market sites that are starting up unrelated to the trial as well – thus, this step (aside from the randomization) is not different than would/does occur normally with mobile market start-up at a new location.

(2) Full-service mobile market implementation (the beginning of the intervention): After initial community engagement, the intervention will begin. Specifically, the market will visit intervention sites weekly. The market will carry items from all food groups including

SOCIAL PROTOCOL (HRP-580)

PROTOCOL TITLE: Mobile Food Market Cluster Randomized Trial

VERSION DATE: 1/5/2023

fresh, frozen and canned fruits and vegetables, whole grains, dairy / dairy substitutes, proteins (e.g., frozen meat/fish, beans, eggs), and dry goods (e.g., cooking oil, spices). Foods will be priced below the cost of local supermarkets (~10% below) and purchases can be made with cash, SNAP/EBT, or credit/debit. The state funded Market Bucks program will provide a dollar-for-dollar match, up to \$10, for produce purchases made with SNAP benefits. Customers will be able to enroll in a “Market Members” loyalty card program that provides incentives for shopping more frequently (e.g. \$5 off every third trip) and all customers will be asked at the point of sale if they are a Member. Community engagement will continue during this time; market staff will check in with site partners regularly to ensure smooth service, addressing any challenges and capitalizing on opportunities (e.g., community events to promote the market) in real time. Intervention site participants will be contacted monthly (e.g., sent a newsletter on the market offerings/sales) in addition to retention contacts described above.

[figure not shown]
As a note, this the start-up and implementation of the mobile market occurs at new Mobile Market sites that are starting up or that are receiving ongoing service unrelated to the trial as well – thus, this step (aside from the randomization) is not different than would/does occur normally with mobile market start-up at a new location.

Waitlist control. Sites randomized to the waitlist will not receive market service prior to follow-up data collection. After follow-up Wave 1 data collection, Wave 1 waitlist sites will participate in community engagement and then receive the market. After follow-up Wave 2 data collection, Wave 2 waitlist sites will do the same. After follow-up Wave 3 data collection, Wave 3 waitlist sites will do the same. The use of a waitlist control was purposeful and informed by our community partners. We will be in communication with waitlist site participants during the 6-month implementation period at the intervention sites, as described above to ensure up-to-date contact information and to facilitate engagement/retention.

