Fruit & Vegetable form completion for 4 weeks		x		x	
Personal, social, behavioral, and environmental factors survey		x		x	
Demographics		x			
Randomization**		x			
Adverse Events		x	x	x	
Mobile market shopping purchases (intervention participants only)			x		
Quantitative measures of mobile market factors that may influence shopping adoption (intervention participants only)				x	
Qualitative interviews with a subset of intervention participants (high & low adopters)					x
Process measures			x	x	

** Randomization occurs after site recruitment for the Wave is complete (about 2 months prior to the end of data collection for the wave. Sites (and the participants attached to those sites) will be randomized to receive mobile market service or to the waitlist (to receive mobile market service after data collection for the wave is complete). After randomization, the study statistician will be unblinded to site names by being provided access to the key that matches sites with their assigned numbers. This will inform him which sites were randomized to the intervention and waitlist control. The study statistician will inform the mobile market co-investigator of the sites randomized to the intervention approximately 2 months prior to the end of data collection to allow time for the mobile market to plan for market routes and schedules. Participants, site locations, the PI, and other UMN trial investigators and staff will be blinded to (i.e., not be informed of) site randomization results until after baseline data is collected. The mobile market co-investigator will explicitly instruct the market drivers (who will help plan the routes with the new stops for the trial sites) that the knowledge of sites is strictly confidential until after baseline data collection is complete and contact between mobile market staff (aside from the Mobile Market co-investigator) and research team, PI, and University staff will not occur during this time to reduce any potential for unintentional disclosure.

Diet quality will be measured through 24-hour dietary recall interviews. Trained staff certified in collecting diet recalls using Nutrition Data System for Research (NDSR) will collect three 24-hour recall interviews (2 weekdays, 1 weekend day)

SOCIAL PROTOCOL (HRP-580)

PROTOCOL TITLE: Mobile Food Market Cluster Randomized Trial

VERSION DATE: 1/5/2023

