from each participant at both measurement periods (baseline, follow-up). At each measurement, the first recall will be conducted in-person during data collection visits; the second two recalls will be by phone. NDSR,⁹⁴ a diet analysis software developed and maintained by the University of Minnesota Nutrition Coordinating Center (led by co-investigator [name]) will be used to collect recalls. The multiple-pass interview technique will be used to prompt for complete recalls and descriptions.⁹⁵ A Food Amounts Booklet adapted from Van Horn et al.⁹⁶ will be provided to participants for use in estimating food and beverage amounts (attached).

To measure diet quality, Healthy Eating Index-2015 (HEI-2015) total and components scores will be calculated from the recall data. The HEI-2015 is a scoring system to measure adherence to the 2015-2020 Dietary Guidelines for Americans (2015-2020 DGA).^{69,70} The HEI-2015 total score is the sum of 13 subcomponents that measure adequacy (Total Fruits, Whole Fruits, Total Vegetables, Greens and Beans, Whole Grains, Dairy Products, Total Protein Foods, Seafood and Plant Proteins, and Unsaturated:Saturated fats) and moderation (Refined Grains, Sodium, Added Sugars, and Saturated Fats). All subcomponents are scored from 0-5 or 0-10 based on intake between minimum and maximum standards. Moderation components are reverse scored so higher scores reflect lower intake. A higher HEI-2015 score (out of 100) represents greater consistency with the 2015-2020 DGA. Additional diet outcomes from recall data include mean daily intake of: energy, fruits and vegetables (servings/day), added sugar (% calories from added sugar) and sodium (mgs/day)..^{69,70} See dietary recall protocol.

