Process Measures (RE-AIM alignment)	Collection Method	Data collected	Who / When	Analysis
Site mobile market operation implementation fidelity (I)	Assessments for deviations in scheduled operation (e.g., related to weather, traffic, repairs), stocking practices, and pricing.	
 Documented deviations (see Fidelity Bus Operations Data Collection Protocol) 	Regularly monitored by study staff during the implementation period	Descriptive
Site sales: use and reach by site (R, A)	The cloud-based, electronic, point-of-sale, cash register records all sales transactions.	
 Date, time, site of sale, payment type, and foods items/categories sold for all transactions (data to be collected are not identifiable or linked to participants – rather this data will be used to describe sales at intervention sites and make comparisons to waitlist and other non-research sites) 	Downloaded monthly by study staff during the implementation period	Descriptive. Total sales and sales by food category for intervention sites
Contamination and dose— self-reported (R, A)	Survey will include questions to assess market dose and contamination exposure	
 Shopping frequency Length of time shopping at the mobile market (in months) (see Process Follow-up Survey) 	Study participants at follow-up data collection	Descriptive and as described in Aim 1 analysis plan
Contamination and dose— objective (R, A)	Fruit and vegetable purchase data collection	Number of trips to Mobile Market	Study participants at baseline and follow-up data collection	Descriptive and as described in Aim 1 analysis plan
Intervention participant market purchases (R, A, M)	Point of sale system with customer loyalty program (Market Members) to track purchases ^a	
 Frequency of purchases Dollars spent on market purchases Number and types of items purchased (see Mobile Market purchasing protocol) 	Intervention site participants during the implementation period	Descriptive and as described in Aim 2 analysis plan

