Key features and suggestions for improvement from intervention participants (A, I)	Open-ended qualitative process survey and interviews about key features that make the market helpful and suggestions for improvement	
 Open-ended responses (see process survey) Qualitative interview transcripts (see qualitative question guide) 	Intervention site participants at follow-up data collection and intervention site participants selected for interviews	See Aim 3

Notes: ^aIntervention site participants will all be enrolled in the Market Member program as part of their participation in the study. All Mobile Market customers, regardless of whether they are at a research site or are participating in the research study, can enroll in this program and receive nominal discounts (\$5 off) every 3-4 shopping trips (see Mobile Market purchasing data collection protocol attachment).

5.3 Randomization: The sites recruited for the trial will be randomized to mobile market service first or the waitlist control (to receive mobile market service after the data collection for each wave is complete). The randomization will be completed by the study statistician who will be blinded to the study site location names. After randomization, the study statistician will be unblinded to site names by being provided access to the key that matches sites with their assigned numbers. This will inform him which sites were randomized to the intervention and waitlist control. The study statistician will then inform the mobile market co-investigator of the sites randomized to the intervention approximately 2 months prior to the end of data collection to allow time for the mobile market to plan for market routes and schedules. Participants, site locations, the PI and other UMN trial investigators and staff will be blinded to (i.e., not be informed of) site randomization results until after baseline data is collected. Of note, only the project manager and the study

statistician will be aware of the key (the link between the site names and the assigned site numbers that will be used in analysis) until analysis is complete.

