VERSION DATE: 1/5/2023

- Because the study will be recruiting in the community, no prisoners will be included.
- No individuals less than 18 years of age are included based on inclusion criteria.
- We do not anticipate enrolling individuals with impaired capacity to consent. Assessment of capacity to consent will be informally made during routine interactions with participants. No specific assessment or documentation of capacity is required under those circumstances.
- American Sign Language speakers will be allowed to participate in this study, though they will not be specifically targeted for recruitment. If an ASL speaker indicates interest in the study while we are conducting recruitment, we will contact a certified interpreter to facilitate communication. An interpreter will be used for all study visits and be available to the participant if they have questions regarding any written forms. We will have an interpreter translate our consent form into a video, a link to which will be provided on the English consent form. In addition, if preferred by the participant, we will allow ASL speakers to conduct their follow-up dietary recalls in person with an interpreter rather than requiring these to be conducted by phone and will allow the interpreter to interpret the iPad written survey questions as read by a study staff member and the participant's responses so they can be entered. Additional non-English speakers may be targeted for recruitment at a later time, but the languages are not yet known. We will amend this protocol/procedures and all related documents once the languages are solidified to add this inclusion criterion and related supporting documentation (e.g., consent form in selected languages etc) and will wait to receive IRB approval related to this modification prior to enrolling participants who do not speak English.

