PROTOCOL TITLE: Mobile Food Market Cluster Randomized Trial

VERSION DATE: 1/5/2023

Data storage. Data for this study will be collected using web-based REDCap survey or with paper-pen that will be entered into a REDCap database, which uses a MySQL database via a secure web interface with data checks used during data entry to ensure data quality. REDCap includes a complete suite of features to support HIPAA compliance, including a full audit trail, user-based privileges, and integration with the institutional LDAP server. The MySQL database and the web server will both be housed on secure servers operated by the University of Minnesota Academic Health Center's Information Systems group (AHC-IS). The servers are in a physically secure location on campus and are backed up nightly, with the backups stored in accordance with the AHC-IS retention schedule of daily, weekly, and monthly tapes retained for 1 month, 3 months, and 6 months, respectively. Weekly backup tapes are stored offsite. The AHC-IS servers provide a stable, secure, well-maintained, and high-capacity data storage environment, and both REDCap and MySQL are widely-used, powerful, reliable, well-supported systems. Access to the study's data in REDCap will be restricted to the members of the study team by username and password. The electronic deidentified data will be downloaded from the Redcap and stored in Box in a password-protected file structure, password-protected server.

NDSR is a software program that will be used to collect dietary recall interviews from participants and assess nutritional quality of participant food purchases. For recalls, the data stored in NDSR is deidentified in that it will contain participant first name (so the interviewer can greet the participant by name), participant study ID number, date of dietary recall interview/fruit & vegetable form, participant sex, recall number (first, second, or third), dietary data, any notes about the recall interview/fruit & vegetable form, and staff who completed the recall. Similarly, for fruit and vegetable form data entry, the data stored in NDSR will contain participant study ID number, sex, date & location of purchase, which purchase form it was (i.e., week 1, 2, 3, or 4), dietary data, any notes about the form, and staff who completed the data entry. These deidentified dietary data will be extracted from NDSR and stored on Box.

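### Blinding of university staff ends after baseline, and the available text does not mask follow-up dietary recall interviewers, although two of the three recalls behind HEI-2015 are by phone

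*Combined protocol and SAP*

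**What the plan says.** Section 4.1 (initial community engagement) sets the reveal: "site group assignment will be revealed for participants and the UMN research team after baseline data collection for the wave is complete". The note under the timeline table in section 5.2, repeated in section 5.3, puts the end of blinding at the same point: "other UMN trial investigators and staff will be blinded to (i.e., not be informed of) site randomization results until after baseline data is collected". That rule covers the PI as well. Section 5.1 places follow-up after six months of market service, so it falls after the reveal.

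Section 3.1 describes who measures the primary outcome: "Trained research staff certified in collecting dietary recalls using Nutrition Data System for Research software will collect three 24-hour dietary recall interviews", at baseline and again at follow-up. Section 5.2 adds that interviewers use the multiple-pass technique to prompt for completeness, and gives the mode used in both periods: "the first recall will be conducted in-person during data collection visits; the second two recalls will be by phone". Section 10.2 makes an exception to the phone calls for those who prefer it: "we will allow ASL speakers to conduct their follow-up dietary recalls in person with an interpreter rather than requiring these to be conducted".

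One restriction lasts beyond baseline. Section 5.3 keeps the list matching sites to numbers with two people, the project manager and the statistician, through the end of the analysis: "statistician will be aware of the key (the link between the site names and the assigned site numbers that will be used in analysis".

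**The concern.** Participants will know whether the market comes to their site, and diet is self-reported, so those sources of bias cannot be designed out. The interviewer's contribution can be reduced. Prompting is part of how a multiple-pass recall is obtained, and an interviewer who knows that a participant has had the market for six months may probe differently, for example for fruit and vegetables.

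The primary analysis in section 17.3 compares within-person change between arms. With interviewers masked at baseline, an interviewer effect that differs by arm at follow-up passes straight into that comparison. Neither the GEE model nor multiple imputation would remove it.

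The protocol takes care over concealment during baseline: market drivers are told to keep the sites confidential, and contact between market staff and the research team is cut. That protection stops before the follow-up outcome is measured.

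**Working it through.** **1. Who is masked, and when.** The relevant sections, side by side:

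| Stage | What the text says | Recall interviewers |
|---|---|---|
| Baseline recalls | Staff not informed of allocation (5.2, 5.3) | Masked |
| After baseline for the wave | Assignment revealed to participants and the university research team (4.1) | Not named, but within the stated group unless an exception exists elsewhere |
| Follow-up recalls | No masking statement in 3.1, 4.1, 5.2, 5.3 or 5.4 | No masking stated |
| Analysis | Site-name key restricted (5.3) | Not affected |

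The key restriction hides which site a number stands for in the analysis data. It does not hide the arm from an interviewer who has already been told it.

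**2. Which recalls could be masked.** Three recalls per participant per period, one in person and two by phone. So 2/3 of follow-up recalls are by phone, or somewhat less once in-person recalls for ASL participants are allowed for.

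**3. Is a masked phone call plausible?** Section 19.1 lists what the NDSR recall record holds: first name, then "participant study ID number, date of dietary recall interview/fruit & vegetable form, participant sex, recall number (first, second, or third), dietary data", followed by notes and the staff member. Neither site nor arm is a listed field. Study IDs are assigned sequentially, with no stated site code. Masking is therefore plausible, but other routes to the arm exist:
- Free-text notes are part of the recall record.
- Fruit and vegetable forms, also entered in NDSR, carry the place of purchase, and the four-week form period overlaps the phone recalls.
- Study staff download site sales and monitor market operation (5.2), and university staff extract loyalty-card purchases (19.1).

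An interviewer who also does any of these tasks for a site could learn its arm.

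**4. The in-person recall.** Market-feature items go only to intervention participants at follow-up (3.2, 5.4), and high and low market users are invited to interviews at that visit (12.3). Visit staff can therefore usually tell the arm. The order of recall and survey is not stated.

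**5. Scale.** The plan's own power statement comes first, as context. Inputs: 224 analysed in 12 clusters and a 5.0-point difference (11.1); SD 12, ICC 0.01, two-sided 5% (17.2).
- Mean cluster size 224/12 = 18.7; design effect 1 + 17.7 × 0.01 = 1.177.
- SE of the arm difference = 12 × √(2 × 1.177/112) = 1.74 points.
- Power for 5.0 points = Φ(5.0/1.74 − 1.96) = 0.82. The stated 80% reproduces.

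The documents give no size for interviewer bias. Purely as an assumption, suppose it shifts the arm difference by b points with no true effect. The rejection rate is Φ(b/1.74 − 1.96) + Φ(−b/1.74 − 1.96):

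| Assumed b (HEI points) | Rejection rate |
|---|---|
| 0 | 5.0% |
| 1 | 8.9% |
| 2 | 21.0% |
| 3 | 40.7% |

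This shows only that a shift well below the 5.0-point target would matter. It says nothing about how large the shift is, or how much of it masking would remove.

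**The case against.** The strongest reply is that the reveal sentence names no interviewers. Conduct of the recalls is delegated to a dietary recall protocol supplied as an attachment, which may already deal with masking. This stands: that interviewers are told is an inference from the reference to the research team and staff, so the point is limited to what the available text shows.

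Second, prompting is already standardised: certified staff, NDSR, the multiple-pass technique and a food amounts booklet. These are real protections and they narrow the room for interviewer bias. They do not make the interviewer unaware of the arm.

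Third, participants may disclose their arm on the phone. That is true, and it limits the gain without abolishing it.

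A reader might also infer several stronger things that the documents do not support:
- **That masking could be done with existing staff and no extra cost.** The number and division of interviewers are not given, the facilities and resources document is an attachment, and each wave has four sites measured simultaneously.
- **That a phone recall needs only a study ID.** The record also holds a first name and notes, and a call needs a phone number.
- **That masking two of three recalls would remove two-thirds of the bias.** This assumes that HEI behaves as a simple average over recalls, that masking is perfect and that all the bias is the interviewer's. None of these is stated.
- **That the dose and contamination row of the process table ("Survey will include questions to assess market dose and contamination exposure") exposes the arm by itself.** Those questions go to study participants generally, and surveys are completed by participants on an iPad. The arm-specific items are the market-feature questions in 3.2 and 5.4.

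**Conclusion.** The point holds in a limited form. The protocol ends staff blinding after baseline, and the available text contains no provision to keep follow-up recall interviewers masked, although interviewer prompting feeds the primary outcome and two of the three recalls are by phone. This is a modest, worthwhile improvement in design, not a flaw that invalidates the trial.

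The size of any bias is unknown and no reduction figure should be attached to the change. The benefit is confined to interviewer-side bias. The conclusion rests on two assumptions: that recall interviewers belong to the research team to whom allocation is revealed, and that the dietary recall protocol does not already mask them. Sample size, power and type I error specifications are unaffected.

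**What to change.** In sections 4.1, 5.2, 5.3 and 5.4:

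1. Replace the reveal to the whole university research team with a reveal to those staff who need allocation for site work.
2. Where current staffing allows, assign follow-up phone recalls to certified interviewers who are not told site or arm and who do not handle that site's visits, sales data or purchase forms.
3. At the follow-up visit, complete the in-person recall before the process survey and market-feature questions.
4. Record any unmasking for each recall, and report recalls done unmasked as a limitation.

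If the dietary recall protocol already covers any of this, a cross-reference in these sections is enough for that part.

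The cost is tighter scheduling of interviewers and a fixed order at the follow-up visit. Whether more staff would be needed cannot be judged from the documents, which is why step 2 is conditional. Some unmasking will remain through participant disclosure and in-person recalls, including those of ASL participants.
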